1.7 Reproductive Health Related Endocrine Disruption in Cancer Care

Rev. Add10

We propose a 2-year observational study following tumor markers for fertility status and endocrine disruption of the first 200 individuals who agree to participate.

Primary Hypothesis

At least 80% of females will have significant endocrine disruption during chemotherapy.

Background

The sequelae of endocrine disruption may include loss of fertility. Although some cancer therapy modalities induce amenorrhea, many patients undergoing treatment remain fertile. After a short period of chemotherapy-induced amenorrhea, 50% of females younger than 35 years resume menstruation, whereas in older females the risk of amenorrhea is increased due to reduced follicular reserve.⁹ The absence of menstruation does not necessarily indicate lack of ovarian function. Additionally, the possibility of spontaneous recovery of ovarian function has been observed, particularly in cases of ovarian germ cell cancer. A study by Fossa found that cisplatin-based chemotherapy is followed by a recovery of ovarian function in almost all patients.⁹

For patients on chemotherapy who desire fertility, ovarian function should be reassessed periodically. Since menstrual activity is not a reliable index to assess ovarian function, various tests like FSH level, inhibin A or B levels or antimullerian hormone (AMH) and vaginal ultrasonography assessment for number of antral follicles can be used.¹⁰

Knowledge of the functional ovarian reserve may benefit females with cancer prior to making important decisions regarding treatment, fertility preservation, and contraception. An ideal marker for fertility status has not yet been identified. Recent literature (2009) indicates the best biochemical indicators of ovarian reserve are serum FSH levels, AMH and Inhibin B.¹¹ In the reproductive

endocrinology literature, AMH is emerging as the optimal marker to determine ovarian reserve and subsequent pregnancy success.¹² Experience with AMH in cancer survivors is limited, however this marker has potential as an indicator of ovarian function post chemotherapy.^{11,13} FSH as a marker may be less reliable as it is ovulatory cycle dependent and affected by tamoxifen and other hormonal therapies.¹³

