3.1 Eligibility Criteria

Rev. 11/17	_____ 3.1.1	Female patients presenting with initial diagnosis of any type of cancer, including patients with DCIS.
Rev. Add8	_____ 3.1.2	Patients must not have initiated chemotherapy, radiation therapy or endocrine therapy prior to registration to this study.
Rev. 11/17	_____ 3.1.3	Patients must not have had a prior hysterectomy, bilateral oophorectomy or sterilization of any method.
Rev. Add9	_____ 3.1.4	Patients must be pre-menopausal patients within the reproductive age range of 15-55 years. Please note, pre-menopausal will be defined as females meeting the following criteria: 
• Patients not currently on hormonal contraception with the presence of menses in the past 6 months.• If no menstruation in the past 6 months, without hormonal manipulation, then confirmed FSH < 23mIU/mL• If age < 47 years and on hormonal contraception, then patient will be eligible regardless of menstrual history• If age ≥ 47 years and on hormonal contraception, then FSH confirmed < 23mIU/mL
Rev. Add10	_____ 3.1.5	Pregnant females are eligible to participate in this study.
Rev. Add10	_____ 3.1.6	Patients must have the cognitive ability to participate in the study.

Rev. 11/17 4. CTEP Registration Procedures

Rev. Add8
Rev. Add11

Food and Drug Administration (FDA) regulations and National Cancer Institute (NCI) policy require all individuals contributing to NCI-sponsored trials to register and to renew their registration annually. To register, all individuals must obtain a Cancer Therapy Evaluation Program (CTEP) Identity and Access Management (IAM) account (<https://ctepcore.nci.nih.gov/iam>). In addition, persons with a registration type of Investigator (IVR), Non-Physician Investigator (NPIVR), or Associate Plus (AP) must complete their annual registration using CTEP's web-based Registration and Credential Repository (RCR) (<https://ctepcore.nci.nih.gov/rcr>).

RCR utilizes five person registration types.

- IVR — MD, DO, or international equivalent;
- NPIVR — advanced practice providers (e.g., NP or PA) or graduate level researchers (e.g., PhD);
- AP — clinical site staff (e.g., RN or CRA) with data entry access to CTSU applications (e.g., Roster Update Management System (RUMS), OPEN, Rave,);
- Associate (A) — other clinical site staff involved in the conduct of NCI-sponsored trials; and

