8.6.3 Plan for Endocrine Disruption in Cancer Care

Rev. Add11

A longitudinal observational study is proposed to examine reproductive health biomarkers in a subgroup of participants (first 200 subjects who agree to participate in this part of study) in the EROS Trial. Participants will be asked to provide blood samples for laboratory correlates (AMH, FSH, TSH, TPO), indicating reproductive health, fertility status, and endocrine disruption. Blood samples will be obtained at baseline and periodically at 3, 6, 12, and 24 months from baseline visit on the study, which totals 8 blood draws. In addition, blood samples will be acquired in conjunction with chemotherapy (within one week of each regimen, prior to chemotherapy) or radiation therapy (within one week prior to the initiation of radiation therapy then every four weeks until the end of radiation treatment). This will increase the number of samples for that population as we attempt to

assess impact of chemotherapy on endocrine function. The hormonal levels at each measurement point will be summarized (by median and range) and plotted across time by marker. All analysis will be performed for patients with chemotherapy and without chemotherapy separately. To assess the impact of chemotherapy on endocrine function, a linear mixed-effect model will be used to make comparisons between the two groups with respect to each marker.

To determine the percent of females having significant endocrine disruption during chemotherapy, Table 7 below summarizes the abnormal level for each marker.

Table 7: Endocrine Markers and Associated Threshold Values for Endocrine Disruption

Marker	Age Range	Abnormal Range
FSH	15-55	≥ 23.0 mIU/mL
TPO	15-55	< 35 IU/mL
TSH	≤ 19	0.50-4.30 mIU/mL
	≥ 20	0.40-4.50 mIU/mL
AMH	≤ 19	0.76 – 11.34 ng/mL
	20-29	0.76- 11.34 ng/mL
	30-39	< 9.24 ng/mL
	40-49	< 4.50 ng/mL
	≤ 50	< 0.45 ng/mL

Quest Diagnostics Laboratory reference ranges

For each marker, the patient with the observed lab value falling into the abnormal range is considered to represent a case with endocrine disruption. Frequency and percentage (along with its 95% confidence interval) will be used to summarize patients with endocrine disruption during chemotherapy for each marker.

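### The last AMH age band in Table 7 is printed as ≤ 50, apparently a reversed sign, so AMH disruption is not uniquely defined at ages 15–49 and has no criterion at 51–55

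*Combined protocol and SAP*

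**What the plan says.** Section 8.6.3 gives Table 7 a specific job: "To determine the percent of females having significant endocrine disruption during chemotherapy, Table 7 below summarizes the abnormal level for each marker". The rule that follows is: "For each marker, the patient with the observed lab value falling into the abnormal range is considered to represent a case with endocrine disruption". For each marker, the number and percentage of such patients are then reported with a 95% confidence interval.

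The AMH part of Table 7 has five rows. The age labels are ≤ 19, 20-29, 30-39 and 40-49, followed by a last row that reads "≤ 50 < 0.45 ng/mL". The first two rows carry the limits "0.76 – 11.34 ng/mL", the third < 9.24 ng/mL and the fourth < 4.50 ng/mL.

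Section 3.1 sets the age range: "Patients must be pre-menopausal patients within the reproductive age range of 15-55 years". The FSH and TPO rows of Table 7 use the same 15-55 range. The sub-study covers the "first 200 subjects who agree to participate in this part of study", and its primary hypothesis in section 1.7 is: "At least 80% of females will have significant endocrine disruption during chemotherapy".

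**The concern.** A table that turns a laboratory value into case or non-case should place each patient in exactly one row. The AMH rows do not. The last row is in the position of the oldest age group, but its label takes in everyone up to 50 and leaves out everyone older.

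Two things follow if the table is programmed as printed. A woman aged 51–55 has no AMH criterion, so she either drops out of the AMH percentage or is handled by a rule that the plan does not contain. A woman under 50 falls in two rows, and for part of the AMH range those rows give opposite answers. The document gives no rule for choosing between overlapping rows and no AMH age bands anywhere else. The reported AMH percentage could then depend on a programming decision that was not specified in advance.

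**Working it through.** The plan gives no figure to reproduce here. The check is a count of ages against row labels, followed by a comparison of the limits.

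**Inputs.** Ages 15 to 55 (section 3.1), which is 55 − 15 + 1 = 41 single-year ages. The five AMH rows are as printed in Table 7.

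**Step 1: rows matched by each age, as printed.**

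- 15–19 (5 ages): ≤ 19 and ≤ 50, two rows.
- 20–29 (10 ages): 20-29 and ≤ 50, two rows.
- 30–39 (10 ages): 30-39 and ≤ 50, two rows.
- 40–49 (10 ages): 40-49 and ≤ 50, two rows.
- 50 (1 age): ≤ 50 only, one row.
- 51–55 (5 ages): no row.

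Two rows: 5 + 10 + 10 + 10 = 35 ages. One row: 1. No row: 5. Total: 35 + 1 + 5 = 41.

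**Step 2: AMH values on which the two matching rows disagree.** A value is in conflict when it lies inside the printed range of one row and outside that of the other.

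- Ages 15–29 (0.76 to 11.34 against < 0.45): conflict below 0.45 and from 0.76 to 11.34 ng/mL. The rows agree from 0.45 to below 0.76 and above 11.34.
- Ages 30–39 (< 9.24 against < 0.45): conflict from 0.45 to below 9.24 ng/mL.
- Ages 40–49 (< 4.50 against < 0.45): conflict from 0.45 to below 4.50 ng/mL.

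**Step 3: does this depend on what the range column means?** The column is headed as abnormal values, while the footnote calls the same figures the laboratory's reference ranges. If the printed ranges are normal rather than abnormal, every case becomes a non-case and the reverse, on both rows at once. A value inside one range and outside the other is still classified oppositely, so the conflict intervals in step 2 are unchanged. What changes is which row calls the woman a case. At age 35 with AMH 2.0 ng/mL, the 30-39 row makes her a case under the heading and a non-case under the footnote, and the last row does the opposite each time.

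**Step 4: the same count with the last label read as ≥ 50.** The rows take 5, 10, 10, 10 and 6 ages (15–19, 20–29, 30–39, 40–49, 50–55). These sum to 41, with each age in exactly one row.

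**Step 5: ages during follow-up.** Samples are drawn up to 24 months after baseline (section 5.9). A patient aged 55 at registration is 55 + 2 = 57 by then, and footnote 7 to the data collection table in section 7 foresees patients who pass 55 on study. If age at the draw is used, a band closed at 55 would leave those samples without a row, whereas an open band ≥ 50 would not.

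**The case against.** The best reply is that the slip corrects itself. Only one reading of the last row makes the five rows a clean division of the age range, and few analysts would score a 25-year-old on the last row when a 20-29 row exists. That stands, and it makes a wrong result less likely. It does not remove the need for a correction, because a case definition fixed in advance should not rely on inference, least of all in a table whose heading and footnote also disagree.

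A second reply is that the sign may have been lost when the PDF was read. This cannot be fully excluded, but it is unlikely: the same table shows ≥ correctly in the FSH limit (≥ 23.0) and in the TSH age label (≥ 20).

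A third reply is limited reach, and it stands. AMH medians, ranges and plots, and the mixed-model comparison of patients with and without chemotherapy, use the measured levels and do not need Table 7. Section 9.2 says that results are not returned to institutions or patients, so no care decision rests on the label.

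A reader might infer more than the documents support. The fraction 35/41 (85%) counts ages and not patients, so it is not the share of the sub-study at risk of misclassification. The number of sub-study patients aged 51–55 is not given either. Nor can one say that a particular woman is wrongly counted as a case, because that depends on the unresolved meaning of the range column. AMH's importance should not be overstated: section 1.7 describes it as emerging as the best marker in the reproductive endocrinology literature, but adds that no ideal marker has been identified and that experience in cancer survivors is limited.

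**Conclusion.** The point holds as a labelling error in an operative threshold. Read literally, Table 7 assigns two AMH rows to ages 15–49, one to age 50 and none to ages 51–55, so the AMH disruption percentage is not uniquely defined and the oldest women cannot be classified on that marker.

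The consequence is confined to the AMH percentage and its confidence interval in the endocrine sub-study, and to whatever weight that percentage carries for the 80% hypothesis. The documents do not support a claim that the primary endpoint, the sample size or the comparison of arms is affected. They also do not allow the shift in the AMH percentage to be estimated.

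The conclusion assumes that the printed sign is the sponsor's own. It also assumes that AMH bands are not redefined in Addendum II, which section 8.1 cites for endpoint details and which is not in the document reviewed. That ≥ 50 was intended is an inference from the order of the bands and the eligibility range. The conflict between column heading and footnote is a separate matter; settling it would leave the age error in place.

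**What to change.** In Table 7, change the last AMH age label from ≤ 50 to ≥ 50. Leave it open-ended and do not cap it at 55. Verify the band and its limit against the laboratory's reference table, and state whether age at registration or age at the blood draw selects the row. Document the correction before the AMH data are classified, ideally together with a resolution of the heading and footnote so that the table is corrected once.

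The cost is one character in the table and a sentence on age. No new data or samples are needed. The sub-study has been closed to accrual since March 10, 2021, and recruitment is not affected.

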7. Pregnancy Test requirements. All patients must be counseled about pregnancy precautions, risks of fetal exposure and other risk as per standard of care. Pregnancy tests should be administered at Baseline, 3, 6, 12, and 24 months from Baseline Visit and within one (1) week prior to each chemotherapy regimen. For patients on radiation therapy (RT) alone, pregnancy tests should be administered within one (1) week prior to the initiation of radiation therapy then every four (4) weeks until the end of radiation treatment. For patients who aged past 55 after enrollment may discontinue pregnancy tests if menopause is confirmed FSH < 23mIU/mL. Patients who have had a hysterectomy after enrollment may also discontinue pregnancy tests. Pregnant patients may discontinue pregnancy tests until delivery

Rev. Add10 8. If patient is pregnant or has been pregnant since her last study visit, one Pregnancy Supplement Form should be completed for each pregnancy.

9. Interview done after visit with the provider.

10. Study surveys should be completed at the beginning of each regimen of cancer treatment. For patients undergoing chemotherapy, surveys should be administered within one (1) week prior to each chemotherapy regimen. For patients on radiation therapy (RT) alone, surveys should be administered within one (1) week prior to the initiation of radiation therapy then every four (4) weeks until the end of radiation treatment. Patients receiving both chemotherapy and RT must follow the chemotherapy reporting schedule; if patient's treatment overlaps (+/- 2 weeks), the questionnaires do not have to be repeated.

Rev. Add10 11. Sites must complete the study surveys within the following windows:

- 3-month visit: +/- one month
- 6-month visit: +/- one month
- starting from 12-month visits: +/- 2 months

12. If there is an overlap (+/- 2 weeks) of visits at 3, 6, 12, and 24 months and visits relating to chemotherapy or RT, the Medical Record Abstraction-Follow up, Patient Follow-up Interview, the Sexual Function Survey and the Pregnancy Test only need to be completed once at the 3, 6, 12, and 24 month visits and not at the chemotherapy or RT visits.

13. The term 'regimen' is defined as anytime a patient starts a new course of medical treatment

Table 2. Biological Sample Submissions

NOTE: Effective March 10, 2021 the endocrine marker sub-study is closed to further accrual. This sub study has met its targeted accrual goal.

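### Table 7 lists laboratory reference ranges as abnormal ranges, so the disruption rule runs backwards for TSH, TPO and AMH to age 29 and over-counts AMH from age 30

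*Combined protocol and SAP*

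**What the plan says.** Section 1.7 gives the primary hypothesis of the endocrine sub-study: "At least 80% of females will have significant endocrine disruption during chemotherapy". Its background says that "AMH is emerging as the optimal marker to determine ovarian reserve".

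Section 8.6.3 sets out how the percentage is to be obtained. It says that "Table 7 below summarizes the abnormal level for each marker" and then gives the rule: "For each marker, the patient with the observed lab value falling into the abnormal range is considered to represent a case with endocrine disruption". Frequency, percentage and a 95% confidence interval follow for each marker.

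The Table 7 column is headed as the abnormal range and contains:

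| Marker | Age band | Printed range |
|---|---|---|
| FSH | 15–55 | ≥ 23.0 mIU/mL |
| TPO | 15–55 | < 35 IU/mL |
| TSH | ≤ 19 | 0.50–4.30 mIU/mL |
| TSH | ≥ 20 | 0.40–4.50 mIU/mL |
| AMH | ≤ 19 and 20–29 | 0.76–11.34 ng/mL |
| AMH | 30–39 | < 9.24 ng/mL |
| AMH | 40–49 | < 4.50 ng/mL |
| AMH | printed as ≤ 50 | < 0.45 ng/mL |

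The line under the table reads "Quest Diagnostics Laboratory reference ranges".

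Two other places bear on the direction of FSH. Section 3.1.4 lists, among its pre-menopausal criteria, "If no menstruation in the past 6 months, without hormonal manipulation, then confirmed FSH < 23mIU/mL". Footnote 7 to Table 1 in Section 7 says that certain patients "may discontinue pregnancy tests if menopause is confirmed FSH < 23mIU/mL".

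**The concern.** The heading and the rule treat each range as the abnormal zone. The footnote says that the figures are laboratory reference ranges, which describe expected values. Both cannot be true of the same numbers, and nothing elsewhere in the documents settles which is meant.

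The outcome at risk is the percentage of patients disrupted on each marker, the sub-study's only planned result that speaks to its 80% hypothesis. If the rule is programmed as written, the TSH and TPO percentages fall as true disruption rises, and so does AMH to age 29. From age 30 the AMH percentage sits near its ceiling whether or not ovarian reserve is lost.

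**Working it through.** The plan gives no sample size, power or expected count for these percentages, so there is no figure of its own to reproduce. The check has three steps.

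**Step 1. Apply the printed rule to single values.** The ranges are those of Table 7; the marker values are illustrative.

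| Marker and age | Counted as disruption | Not counted |
|---|---|---|
| TSH, 18 or 35 | 2.0 | 0.1 and 10 |
| TPO, 35 | 5 and 34 | 35 and 300 |
| AMH, 25 | 3.0 | 0.05, 0.5 and 12 |
| AMH, 29 | 3 and 9 | 0.05 |
| AMH, 30 | 0.05, 3 and 9 | none of these |
| AMH, 45 | 0.05, 2 and 4 | none of these |
| FSH, 35 | 23 and 60 | 6 and 22.9 |

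A TSH zone that leaves out both extremes cannot be an abnormal range. The TPO row passes a high antibody level, against the concern with autoimmune thyroid disease in Section 1.7. An AMH of 0.05 is not disruption at 29 but is at 30, so the column is not one consistent set of abnormal zones. FSH alone behaves as its heading says, and it agrees with the Section 3.1.4 check.

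**Step 2. Effect on the reported percentage.** Let *d* be the true disrupted fraction and *c* the share of unaffected women inside the printed range. Assumptions: *c* is 0.90 to 0.95, which the documents do not give; there is one draw per patient; disrupted TSH values lie outside the range; and depleted AMH values lie below the upper limit.

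- TSH: reported fraction = (1 − *d*)*c*.
- AMH from age 30: reported fraction = *d* + (1 − *d*)*c*.

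| True *d* | TSH reported | AMH from age 30 reported |
|---|---|---|
| 0 | 90–95% | 90–95% |
| 0.5 | 45–47.5% | 95–97.5% |
| 0.8 | 18–19% | 98–99% |

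For example, at *d* = 0.8 and *c* = 0.90, TSH gives 0.2 × 0.90 = 0.18 and AMH gives 0.8 + 0.2 × 0.90 = 0.98. Between no depletion and 80% depletion, the AMH figure moves by 4 points (95 to 99) to 8 points (90 to 98).

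If disruption is defined strictly as a value outside the reference range, the rule reports 1 − *p* for a true rate *p*: 80% becomes 20% and 20% becomes 80%.

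**Step 3. Would the confidence interval give a warning?** Take an unaffected group reported at 90%. The Wilson limits are [*p* + *z*²/2*n* ± *z*√(*p*(1 − *p*)/*n* + *z*²/4*n*²)] / (1 + *z*²/*n*), with *z* = 1.96. For 90/100 this is (0.9192 ± 0.0619)/1.0384 = 0.826 to 0.945. The number of chemotherapy patients is not stated (the sub-study enrols 200), so a range is shown:

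| Reported | 95% CI |
|---|---|
| 45/50 | 78.6–95.7% |
| 90/100 | 82.6–94.5% |
| 135/150 | 84.2–93.8% |
| 95/100 | 88.8–97.8% |

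With counts rounded to the nearest whole patient, the lower limit stays above 80% for every *n* from 68 at 90% reported, and from 33 at 95% reported. The value 68 depends on the rounding: it is 62 with unrounded counts and 74 with counts rounded down. An undisturbed group could thus appear to support the hypothesis, with nothing in the interval to expose the error.

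**Related inconsistencies.** The last AMH band, read as printed, overlaps all the younger bands and leaves ages 51–55 without a row, although eligibility runs to 55. Footnote 7 to Table 1 ties FSH below 23 to confirmed menopause, whereas Section 3.1.4 ties it to pre-menopausal status.

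**The case against.** The reversal for TSH, TPO and AMH to age 29 is hard to dispute. The fair objections concern size and scope.

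- **Definition of disruption.** If a value outside the reference range is disruption, the rule reports exactly 1 − *p*, and the 18–19% becomes 20%. The coverage of 90–95% has no source in the documents. This stands as a limit on precision; the direction and rough size do not change.
- **AMH from age 30.** Section 8.6.3 does not say which direction counts, and the documents give no depletion threshold. Over-counting holds if disruption means loss of reserve, as Section 1.7 implies. If it means above the laboratory's upper limit, these rows are reversed too. Lower limits could also have been lost when the PDF was read. The rule needs specifying on any of these readings.
- **No formal test.** The plan gives a percentage and interval per marker, with no test against 80% and no composite across markers. It also schedules several draws per patient. Step 3 therefore shows how the result could be read, not a planned decision.
- **Peripheral items.** The last age band may be a misprint or a reading error, and the Table 1 footnote does not feed the percentages. Both only need checking.
- **An analyst would notice.** Perhaps, because the footnote exposes the conflict. But inverting every row would break FSH and, from age 30, would flag only high AMH. The right rule cannot be inferred from the table.

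**Conclusion.** The concern holds. As written, the rule reverses endocrine disruption for TSH, TPO and AMH to age 29, and from age 30 it counts ordinary AMH values along with depleted ones. On TSH, true disruption of 80% would be reported as 18–19% with the assumed coverage, or 20% on the strict definition, and no disruption as at least 90%. AMH from age 30 would barely separate a depleted group from an intact one. No overall AMH figure can be given, because the age mix is unknown and the two kinds of error combine.

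The reversal follows from the documents alone. The sizes rest on the stated coverage, the one-draw simplification and, for AMH from age 30, on disruption meaning low values. The damage is confined to the per-marker percentages. FSH, the primary endpoint, the sample size, the medians and plots, and the mixed-model comparison are unaffected. It should be fixed before analysis.

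**What to change.** Before the marker data are classified:

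1. Reconcile the heading, footnote and ranges of Table 7, with separate columns for the reference range and the disruption criterion.
2. For TSH and TPO, define disruption as a value outside the reference range. Leave the FSH row in its present direction.
3. For AMH, have the study team and the laboratory state the direction and a lower limit for each age band.
4. Check the last AMH age band, so that the bands do not overlap and ages 51–55 are covered.
5. Reconcile the FSH direction in footnote 7 to Table 1 with Section 3.1.4 and Table 7.

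The cost is low: a wording change and one request for AMH limits, which the documents do not give from age 30. Stored values can be reclassified and no new samples are needed. Settling the criteria before results are seen also avoids cut-offs chosen from the data.

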Additionally alterations in thyroid function have been noted in females with breast cancer with a baseline rate of autoimmune thyroid disease 2-3 times the general population.¹⁴ Thyroid function may be affected by chemotherapy and radiation treatment, particularly when treatment is localized to the vicinity of the thyroid.¹⁵ Such disruption may lead to symptoms that may affect quality of life indicators related to sexuality and sexual health. Repercussions of these effects remain an important aspect of research within oncology care. Given the available data, many questions remain unanswered; therefore, the laboratory ancillary included in this proposal would provide important data during the course of our primary study.

This data will provide a foundation for future research to aid prediction of fertility status throughout the course of cancer care and treatment.

This analysis will be performed at Quest Diagnostics.

Rev. Add9

1.8 Quality of Life (QOL) Assessment: Longitudinal Study of Sexuality in Females with Newly Diagnosed Cancer

Rev. Add11

We propose a prospective observational study performing interval sexuality surveys for reproductive aged females throughout 2 years post diagnosis of cancer.

Hypothesis

Primary Hypothesis: Cancer survivors' sexual function decreases during initial cancer treatment then increases with time after treatment completion.

Secondary Hypothesis: Cancer survivors have lower levels of satisfaction with their sex lives compared to the age-matched general population at baseline.

Background

Sexuality remains an important aspect of reproductive health that is greatly influenced by cancer diagnosis and treatment. The extent of impact of cancer diagnosis and treatment is poorly understood. Sexuality encompasses gender roles, patterns of affection, social and family roles, and genital sex, and affects a survivor physically, psychologically, and emotionally.¹⁶ It should be understood that sexuality is "an ever-changing, lived experience affecting the way in which people view themselves, their body and their ability to intimately connect with significant others throughout life, rather than limiting it to fertility status or capacity for sexual intercourse."¹⁷

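### The endocrine sub-study's 80% hypothesis cannot be answered from the planned output: the case rule ignores the pre-treatment value, and four marker percentages face one patient-level claim

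*Combined protocol and SAP*

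**What the plan says.** - **Hypothesis.** Section 1.7 gives the sub-study one primary hypothesis: "At least 80% of females will have significant endocrine disruption during chemotherapy". It is a statement about women and names no marker. The background in the same section reports, for females with breast cancer, "a baseline rate of autoimmune thyroid disease 2-3 times the general population".
- **Cohort and samples.** Section 8.6.3 takes the "first 200 subjects who agree to participate in this part of study" and measures four markers: AMH, FSH, TSH and TPO. "Blood samples will be obtained at baseline and periodically at 3, 6, 12, and 24 months from baseline visit on the study". Women on chemotherapy also give a sample in the week before each regimen.
- **Case rule.** "For each marker, the patient with the observed lab value falling into the abnormal range is considered to represent a case with endocrine disruption". The abnormal values are those listed in Table 7.
- **Summary.** A frequency and percentage with a 95% confidence interval "will be used to summarize patients with endocrine disruption during chemotherapy for each marker".
- **Other analyses.** Section 8.6.3 also summarises and plots marker levels at each measurement point. A linear mixed model compares levels between women with and without chemotherapy.
- **What is not visible.** Section 8.1 places endpoint details in the statistical analysis plan in Addendum II, which is not part of the available text.

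**The concern.** The hypothesis is about disruption during chemotherapy, which a reader will take as a change brought about in that period. The case rule measures something else: whether a value is abnormal at the time, whatever it was before. A baseline sample is drawn and could separate the two, but the rule does not use it.

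The hypothesis is also a single proportion of patients, while the plan delivers four proportions, one per marker. Without a rule linking them, one reader could judge 80% against AMH alone, another against any marker, and both would be consistent with the text. At stake is whether the sub-study's primary hypothesis gets an answer at all, and whether the reported percentages can be described as disruption arising in treatment.

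**Working it through.** The documents give no sample size, power or precision figure for the 80% hypothesis, so there is no stated figure to reproduce. Every rate below other than the 80% is an assumption for illustration.

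**1. Which samples count.** The baseline draw is on the day of registration, before treatment (Section 9.2). The chemotherapy-linked draw is taken in the week before each regimen (Sections 8.6.3 and 9.2), so the one before the first regimen is still pre-treatment. Section 8.6.3 does not say whether that draw counts, nor how a scheduled draw at 3, 6, 12 or 24 months is classed as during or after chemotherapy.

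**2. Whether entry criteria remove baseline abnormality.** Section 3.1.4 requires FSH below 23 mIU/mL only for women without menses in the past 6 months and without hormonal manipulation, and for women aged 47 or over on hormonal contraception. This is the complement of Table 7's FSH entry (23.0 or above). Women with recent menses, and women under 47 on hormonal contraception, enter without an FSH test. There is no entry criterion for TSH, TPO or AMH. The screen is therefore partial for one marker and absent for three.

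**3. Effect of persisting abnormality on one marker's percentage.** Let b be the fraction abnormal before treatment, s the fraction of those still abnormal during chemotherapy, and i the fraction newly abnormal among women normal at baseline.

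Counted percentage = b·s + (1 − b)·i

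With full persistence (s = 1) and i = 75%:
- b = 10%: 0.10 + 0.90 × 0.75 = 77.5%
- b = 20%: 0.20 + 0.80 × 0.75 = 80.0%
- b = 30%: 0.30 + 0.70 × 0.75 = 82.5%

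In the middle case the newly abnormal women are 0.80 × 0.75 = 60% of all women. Conversely, at s = 1 a counted 80% corresponds to i = (0.80 − b)/(1 − b), which is 77.8%, 75.0% or 71.4% for b = 10%, 20% or 30%.

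The counted figure differs from i by b(s − i). It exceeds i only when baseline abnormality persists more often than new abnormality arises; if s = i the two agree.

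**4. What four marker percentages say about one patient-level event.** For marker percentages p1 to p4, the percentage with any marker abnormal lies between max(p) and min(1, sum of p). Under independence with equal p it is 1 − (1 − p)^4.
- p = 20% each: 20% to 80%; independent, 1 − 0.8^4 = 59.0%
- p = 40% each: 40% to 100%; independent, 1 − 0.6^4 = 87.0%
- p = 33.1% each: independent, 1 − 0.669^4 = 80%. If AMH agreed perfectly with FSH, and TSH with TPO, with the pairs independent, 1 − 0.669² = 55%

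The same four planned outputs are thus compatible with any-marker rates far apart, and on either side of 80%.

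**5. How the comparison with 80% would be made.** Exact (Clopper-Pearson) 95% intervals for an observed 80% are 73.8% to 85.3% at n = 200 and 70.8% to 87.3% at an assumed 100 chemotherapy patients (the size of that subset is not given). For the lower limit to reach 80%, 172/200 (86%) or 89/100 (89%) would be needed. The plan does not say whether the estimate or the limit decides.

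**The case against.** Several points on the other side are fair.

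- **Any abnormal value at any time counts.** A reader might infer this from the case rule read alone. The summary sentence does not support it: the percentage is limited to disruption during chemotherapy, so a value abnormal only at baseline does not by itself count. What stands is abnormality that persists, and the undefined status of the first pre-regimen draw.
- **The favourable marker could be chosen afterwards.** A reader might infer this too, but the plan commits to reporting all four percentages, so it is conjecture. The supported point is narrower: the hypothesis is not linked to any of them.
- **Baseline abnormality may be rare.** The only evidence in the protocol is a relative figure, for breast cancer, on thyroid autoimmunity. Nothing shows how often AMH or FSH is abnormal at entry, and FSH is partly screened.
- **Other analyses show baseline.** The plots display pre-treatment levels, and the mixed model gives a no-chemotherapy comparison. Both are useful context, but neither produces the percentage in the hypothesis.
- **Prevalence may be intended.** The hypothesis can be read as the share of women with abnormality during treatment, whatever its origin. That reading is tenable and is a reason to keep the present percentage. It does not supply the missing patient-level event.
- **Addendum II may define the event.** This cannot be excluded. Section 8.1 gives protection of the intervention as the reason for placing endpoints there. The marker rule is set out openly in Section 8.6.3.

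**Conclusion.** The point holds in this form. As written, the rule counts abnormality that was present before treatment and persists into chemotherapy, it leaves the qualifying samples undefined, and the visible text gives no patient-level event to compare with 80%. The hypothesis therefore cannot be answered from the planned output.

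The second limb follows from the text alone. The size of the first is unknown, because the documents give no baseline abnormality rates. The shift from 75% to 80% in the working rests on assumed values of 20% abnormal at baseline, full persistence, and 75% new abnormality among women normal at baseline. A reader might also take the 33.1% per marker calculation to mean that an any-marker rate of 80% is likely. It needs four independent markers, whereas AMH and FSH both reflect ovarian function and TSH and TPO are both thyroid tests.

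The matter is confined to an observational sub-study and does not touch the trial's primary endpoint.

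**What to change.** First reconcile Table 7. Its column is headed as abnormal ranges but footnoted as laboratory reference ranges, and until that is settled neither a case nor a normal baseline can be identified. Then amend Section 8.6.3, before analysis, to:

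1. Report for each marker the percentage, with 95% confidence interval, newly abnormal after chemotherapy has started among women not abnormal at baseline. Report women abnormal at baseline separately, and keep the present overall percentage as a secondary prevalence summary.
2. State which samples qualify as during chemotherapy, including how the draw before the first regimen is treated.
3. Name one patient-level event, a marker or a stated combination, for the 80% hypothesis, and say how its 95% interval is to be compared with 80%. If Addendum II already defines this, a cross-reference is enough.

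The cost is wording: baseline samples are already scheduled and no new visits are needed. The downside is a smaller denominator, hence a wider interval, and probably a lower percentage if abnormality before treatment usually persists. A single baseline value can also misclassify some women, since Section 1.7 itself describes FSH as cycle dependent; this should be acknowledged when the event is chosen.
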